6. DOSING DELAYS/DOSE MODIFICATIONS

Each vaccination and/or chemokine-modulation regimen may be delayed for up to 8 weeks and all subsequent cycles will be adjusted accordingly.

6.1 Phase 1

Any patient who experiences a RLT will be removed from study treatment and followed until the RLT resolves to Grade 1 or baseline.

6.2 Phase 2

After cycle 1, any AE experienced by a patient must resolve to Grade 1 or baseline prior to receiving adjuvant chemotherapy.

6.2.1 DC vaccine

Any patient who experiences the following, and is attributable to the DC vaccine, will be removed from study treatment:

- Grade 2 or more bronchospasm or generalized urticaria (hypersensitivity)
- Grade 2 or more allergic reaction
- Grade 3 injection site reaction due to vaccine
- > Grade 3 toxicity of any kind related to the DC vaccine

6.2.2 CKM

For grade 3 toxicities:

1st episode: dose will be held (until the toxicity is reduced to \leq grade 1 or baseline) and restarted at the next study visit at a dose reduction of 33% (dose reduction for IFN and rintatolimod, celecoxib will not be dose reduced). The dose can be re-escalated at the next study cycle.

2nd episode: dose will be held and restarted (if toxicity is resolved to \leq grade 1 or baseline) at the next study visit at a dose reduction of 33%. The dose cannot be re-escalated.

For grade 4 toxicities:

1st episode: dose will be held (until the toxicity is reduced to \leq grade 1 or baseline) and restarted at the next study visit at a dose reduction of 33% (dose reduction for IFN and rintatolimod, celecoxib will not be dose reduced). The dose can be re-escalated at the next study cycle.

2nd episode: Eliminate the CKM regimen

Patients who are discontinued from the CKM treatment may still receive the DC vaccine.

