The Phase 2 immunotherapy regimen will include 1 priming dose of the α DC1 vaccine and 3 booster doses of the α DC1 vaccine combined with CKM. Each dose of vaccine, whether priming or booster, will include 1 intranodal (3M cells) and 1 intradermal (3M cells) injection. Phase 1 includes only the priming vaccine dose and 1 cycle of a booster dose + CKM.

Each booster vaccine dose (booster cycles 1-3) will be followed by 4-days of systemic CKM which is comprised of intravenous (IV) IFN α (dose-escalation in Phase 1 only: 5-20 MU/m 2) once a day for 4 days; IV rintatolimod (short-half-life TLR3 ligand) 200 mg on Wednesday and Friday only of the CKM regimen; and oral celecoxib 200 mg twice a day for all 5 days.

In order to avoid overlap between experimental immunotherapy and potential adjuvant chemotherapy (which can be clinically indicated as a part of standard care in a subset of patients), the experimental treatment may be interrupted after each cycle to allow adjuvant chemotherapy that may be done for each patient's clinical care, not as part of this research study. If clinically indicated any cycle of adjuvant chemotherapy may start a minimum of 5 days after completion of a cycle of immunotherapy and recovery from any potential side effects. The following cycle of immunotherapy may start at least 5 days after the completion of chemotherapy and after recovery from acute side effects of chemotherapy.

Timing of the experimental treatment:

- Priming cycle (vaccine alone): 6 to 16 weeks after surgery (target: 8 weeks)
- Booster cycle 1 (vaccine plus CKM): 4 to 12 weeks after priming cycle (target: 4 weeks)
- Booster cycle 2 (vaccine plus CKM): 4 to 12 weeks after booster cycle 1 (target: 4 weeks)
- Booster cycle 3 (vaccine plus CKM): 4 to 12 weeks after booster cycle 2 (target: 4 weeks)

The primary endpoint will be time to tumor progression/recurrence on CT or MR imaging. Secondary endpoints will be immunologic response markers.

UPCI #: 12-110

Version Date: 03-18-2016

The schemas for the trial are located in Sections 5.1 and 5.2.

TABLE OF CONTENTS

SCHEMA.....	2
LIST OF ABBREVIATIONS.....	6
1. OBJECTIVES	8
1.1 Primary Objectives.....	8
1.2 Secondary Objectives.....	8
2. BACKGROUND	8
2.1 Tumor Immunogenicity in Malignant Peritoneal Mesothelioma.....	8
2.2 Tumor Immunogenicity in Colorectal Adenocarcinoma with Peritoneal Carcinomatosis.....	10
2.3 Tumor Immunogenicity in Appendiceal Adenocarcinoma with Peritoneal Carcinomatosis.....	11

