3. PATIENT SELECTION

Consent will be obtained for this study on all eligible patients by the investigator or sub-investigators. No patient will be entered into this clinical trial without having signed a consent form. The research nurse coordinator or designee will screen the patients further, as per investigator/sub-investigator orders, to determine if they meet all the inclusion/exclusion criteria. If a recruited patient is excluded or resigns for any reason during the course of study, a new patient will be enrolled. However, such patients may continue to be followed and/or receive any available vaccine doses.

Candidates for this trial will have peritoneal surface malignancies and CRS + HIPEC is clinically indicated as the first line treatment. Due to the autologous nature of the vaccine, tumor tissue and the cells obtained from the leukapheresis procedure are required. Without those the vaccine cannot be manufactured and the patients are not eligible for this clinical study.

Surgical outcome of must be deemed able to undergo optimal CRS defined as CC-score of 0 or 1 based on post-surgical imaging. Cytoreduction is defined as the burden of residual disease nodules left at the end of surgery (CC-0: no visible disease; CC-1: residual tumor nodules \leq 2.5 mm in size; CC-2: residual tumor nodules 2.5 mm – 2.5 cm in size; CC-3: residual tumor nodules $>$ 2.5 cm in size).

Screening will occur after recovery from surgery to ensure they meet criteria for treatment.

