Study treatment will consist of one priming dose of DC vaccination followed by 3 booster cycles of DC vaccine + chemokine modulation regimen (CKM), cycles 1-3. The booster vaccine is administered on Monday followed by 4 days of the CKM regimen (Tuesday – Friday).

Timing of the experimental treatment:

- Priming cycle: 6 to 16 weeks after surgery (target: 8 weeks)
- Booster cycle 1: 4 to 12 weeks after priming cycle (target: 4 weeks)
- Booster cycle 2: 4 to 12 weeks after booster cycle 1 (target: 4 weeks)
- Booster cycle 3: 4 to 12 weeks after booster cycle 2 (target: 4 weeks)

It is expected that a significant proportion of the patients will undergo adjuvant clinically indicated chemotherapy. Adjuvant chemotherapy can be administered between the courses of immunotherapy, but no sooner than 5 days after finishing any cycle of immunotherapy. The following cycle of immunotherapy will start no sooner than 5 days after the last day of a chemotherapy cycle and after recovery from acute side effect of chemotherapy.

Patients who (for clinical or logistic reasons) will not be able to take any cycle of immunotherapy within the above-indicated windows, can still receive the remaining courses of immunotherapy at later time points, but will not be included in the analysis of the primary efficacy endpoint, although they can be analyzed in an exploratory manner.

Similarly, patients who (for clinical or logistic reasons) will not be able to receive the priming dose of vaccine within 3 months after surgery, can still receive immunotherapy at later time points, but will not be included in the analysis of the primary efficacy endpoint, although they can be analyzed in an exploratory manner.

In the efficacy phase, patients will receive a priming dose of the α DC1 vaccine followed by 3 courses of the α DC1 booster vaccine combined with CKM regimen as illustrated in the following table:

Eligibility	Informed Consent CRS + HIPEC
Screening	History and physical exam, ECOG performance status, blood work, evaluation of tumor material
Post-surgery (within the first 8 weeks following surgery)	Leukapheresis
Week 1* (upon recovery from surgery; no sooner than 6 weeks post-surgery)	Priming Vaccine dose; no chemokine modulation) One day: α DC1 vaccine Oral celecoxib, 200 mg, before and after treatment on the day of vaccination
Weeks 2-3	Rest
Week 4 (target)*	Booster Cycle 1 Monday: α DC1 vaccine

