5.5 Continuation of Booster Vaccines Administration

At the discretion of the treating physician, any patient who completes study treatment or is removed for reasons other than vaccine related AE/SAEs may continue to receive available vaccine. These vaccines may be administered 4-12 weeks apart. Subjects removed will continue to be evaluated for safety, but not be included in the analysis of formal efficacy objectives but may be evaluated in an exploratory manner. These subjects will be evaluated/followed based upon the conventional care evaluations outlined in the study calendar on days of vaccination (i.e., PE, vitals, AE evaluation).

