5.9 Duration of Follow Up

Patients will be followed until death and the follow-up information for trial reporting will be obtained either from the patient's medical records or through direct contact with the patient (i.e. clinic visit or phone call). The timing of these will be based on scheduling of clinical care for the treatment of the patient's cancer (i.e. clinic visits every 3 months, 6 months, yearly). Patients will be followed specifically for evidence of progression/recurrence based on imaging and survival.

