6.4 Hypersensitivity Reactions

Caution: patients who had a mild to moderate hypersensitivity reaction have been successfully re-challenged, but careful attention to prophylaxis and bedside monitoring of vital signs is recommended.

Hypersensitivity reactions to IFN α and/or TLR3 ligand will be managed as follows:

Mild symptoms (e.g., mild flushing, rash, pruritus) - complete infusion, supervise at bedside, no treatment required.

Moderate symptoms (e.g., moderate rash, flushing, mild dyspnea, chest discomfort) - stop infusion, give intravenous diphenhydramine 25 mg and intravenous dexamethasone 10 mg, resume the infusion at a low rate after recovery of symptoms, then, if no further symptoms, at full dose rate until infusion is complete. If symptoms recur, stop the infusion and the patient should receive no additional INF α or TLR3 ligand for that cycle, but may be retreated after discussion with the Investigator. Keep a record of the toxicity.

Severe life threatening symptoms (e.g., hypotension requiring pressor therapy, angioedema, respiratory distress requiring bronchodilation therapy, generalized urticaria) - stop infusion, give intravenous diphenhydramine and dexamethasone as above, add epinephrine or bronchodilators if indicated. If wheezing is present, that is not responsive to bronchodilators, epinephrine is recommended. Patient should be removed from further protocol therapy. Report it as an adverse event.

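### Phase 2: the 6.2.2 restart rule lacks an exception for the severe hypersensitivity that 6.4 treats as grounds for removal, and toxicity stops can take treated patients out of the primary TTP analysis

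*Combined protocol and SAP*

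**What the plan says.** This concerns Phase 2 only. Section 6.1 already takes Phase 1 patients with an RLT off study treatment.

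**Restart and removal**
- Section 6.2.2, first grade 3 or first grade 4 CKM toxicity: hold until grade 1 or baseline, then "restarted at the next study visit at a dose reduction of 33% (dose reduction for IFN and rintatolimod". Celecoxib is not reduced. Re-escalation is permitted at the next cycle. A second grade 4 episode ends CKM, and "Patients who are discontinued from the CKM treatment may still receive the DC vaccine".
- Section 6.4, severe life-threatening hypersensitivity to IFN or the TLR3 ligand: "Patient should be removed from further protocol therapy".
- Section 6.2.1 writes hypersensitivity removal into its own text, but only for events attributed to the vaccine.

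**Analysis status**
- Section 5.5: "Subjects removed will continue to be evaluated for safety, but not be included in the analysis of formal efficacy objectives". They may be examined in an exploratory manner.
- Section 5.2 leaves out of the primary efficacy analysis any patient who "will not be able to take any cycle of immunotherapy within the above-indicated windows". The Schema describes each booster cycle as vaccine and CKM together: "Booster cycle 1 (vaccine plus CKM".
- Section 13.3 analyses evaluable patients and does not define the term.
- Section 3: "If a recruited patient is excluded or resigns for any reason during the course of study, a new patient will be enrolled".

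**The concern.** Sections 6.2.2 and 6.4 govern the same two intravenous drugs. For a severe reaction that is also graded 3 or 4, one says restart at a lower dose and the other says stop for good. Someone who consults only the dose-modification rule could re-expose a patient to IFN or rintatolimod after a life-threatening reaction.

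The second issue is statistical. The primary test compares TTP in one treated arm with literature medians of 20, 20 and 12 months (13.2). Dropping a patient after treatment has begun, because of what the treatment did, conditions the analysis set on a post-treatment event. No equivalent selection can be applied to the historical figures. For the patient who loses CKM but stays on vaccine, inclusion is undefined and could end up being decided once outcomes are known.

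**Working it through.** **1. The two rules side by side.** Section 6.2.2 is triggered by toxicity grade, 6.4 by symptom description (mild, moderate, severe). No text maps one scale to the other or states precedence, and 6.2.2 does not refer to 6.4. The contradiction is confined to severe IFN or rintatolimod reactions that are also graded 3 or 4. For milder reactions both sections allow further treatment.

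**2. Analysis status by route off treatment.**
- Removed under 6.4: excluded from formal efficacy by 5.5. This is settled.
- Removed for vaccine toxicity under 6.2.1: also a removed subject, so 5.5 excludes this patient too.
- CKM eliminated under 6.2.2, vaccine continued: not called removed, so 5.5 does not clearly apply. Section 5.2 would exclude the patient if a vaccine-only booster is not a cycle, but the plan does not say. Section 13.3 does not resolve it.

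**3. The plan's own sample size.** Inputs from 13.2 and 13.3: N = 168, 36 months of accrual, 18 months of further follow-up, ratio 1.25, one-sided alpha 0.10, power 90%, null medians 20/20/12, target medians 25/25/15, case mix 15:40:60 of 115. Assumptions added here: uniform accrual, exponential TTP, no losses.
- Events needed = ((1.2816 + 1.2816)/ln 1.25)² = (2.5631/0.22314)² = 131.9.
- P(progression) = 1 − [exp(−18λ) − exp(−54λ)]/(36λ), with λ = ln 2/median.
- Null medians: 0.694, 0.694, 0.851; weighted 0.776. N = 131.9/0.776 = 170.03, so 171. Power at 168 is 0.897. This reproduces the stated 168 and 90% closely.
- Target medians: 0.616, 0.616, 0.788; weighted 0.7057. Events at 168 = 118.6; power 0.8745. The steps below use this lower baseline. The gap between 0.897 and 0.8745 comes from the choice of event probability and is not part of this point.

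**4. Power if excluded patients are not replaced.** Power = Φ(√d × ln 1.25 − 1.2816), d = 0.7057 × N.
- 1 excluded (1/168 = 0.6%): N = 167, d = 117.8, power 0.8730, a loss of 0.15 points.
- 2 (1.2%): N = 166, d = 117.1, power 0.8715.
- 8 (4.8%): N = 160, d = 112.9, power 0.8620.
- 17 (10.1%): N = 151, d = 106.6, power 0.8466.

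The documents give no rate of stopping for toxicity, so the counts of 2, 8 and 17 are assumptions. If section 3 replaces each such patient, N stays at 168 and power at 0.8745, at the price of extra enrolment.

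**5. Shift in the estimate.** TTP ratio = Σ(null hazard × person-time)/events. Assume a true ratio of 1.25 among retained patients, and an excluded fraction whose progression hazard is 0.5 or 2 times that of the rest.
- 1% excluded: the ratio with everyone kept is 1.2584 (hazard 0.5) or 1.2421 (hazard 2). Excluding them gives 1.25, a change of −0.67% or +0.64%.
- 5% excluded: 1.2926 or 1.2109 with everyone kept; change −3.29% or +3.23%.

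**The case against.** The strongest reply is that section 6 gives a general CKM rule followed by toxicity-specific rules in 6.3 and 6.4, that the specific rule prevails, and that 5.7 separately ends treatment for unacceptable adverse events. That is the right reading, and it reduces the first part to a missing exception. It does not remove it: the protocol nowhere states the precedence, and 5.7 does not define unacceptable. Safety after a life-threatening reaction should not rest on inference.

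Four stronger readings are tempting, and the documents do not support them.
- A reader might take the patient in 2.6.3, with grade 3 flushing and hypotension on CKM, as an instance of the conflict. It is not. The reaction resolved when the rintatolimod infusion was slowed and is not reported as severe in the 6.4 sense, so restart versus removal did not arise. The same section reports that Phase 1 of a similar CKM trial finished without regimen-limiting toxicity.
- A reader might infer that the status of everyone who stops CKM is unsettled. Section 5.5 settles it for removed patients, including 6.4 removals. Only the vaccine-alone patient under 6.2.2 is undefined.
- A reader might infer that the exclusions flatter the treatment. The direction depends on whether excluded patients progress sooner or later than the rest, and nothing in the documents shows which.
- A reader might infer that vaccine doses hang on the choice. After a 6.4 removal, 5.5 still lets the physician give available vaccine, as 6.2.2 does.

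It can also be said that retaining these patients changes the primary analysis set rather than clarifying it. That is correct for removed patients and should be acknowledged in the amendment. It is also why vaccine-toxicity removals must be handled in the same way as CKM-toxicity stops: retaining one group and excluding the other would have no rationale.

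**Conclusion.** Both parts hold, and both are minor. In Phase 2, 6.2.2 as written lacks the exception that 6.4 requires. That is a safety wording gap with an obvious intended answer. In the analysis, 5.5 makes a stated, toxicity-driven exclusion in a single-arm test against historical medians, and one group, vaccine alone after CKM is eliminated, has no stated status.

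The size is small and cannot be fixed from the documents. The loss of about 0.15 power points per unreplaced exclusion rests on the exponential, uniform-accrual model with target-median events. The shift of about 0.7% to 3.3% in either direction rests on assumed exclusion rates of 1% to 5% and assumed hazards of 0.5 to 2 times the rest. Neither figure threatens the design. The case for change is that the rules should be unambiguous before outcomes are known.

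**What to change.** 1. In 6.2.2, except hypersensitivity reactions to IFN or rintatolimod from the hold-and-restart rule, refer them to 6.4, and state that there is no re-challenge after a severe reaction. Leave the removal rule in 6.4 as it is.
2. In 5.2, 5.5 and 13.3, state that treated Phase 2 patients who stop CKM or vaccine because of toxicity (6.2.1, 6.2.2 or 6.4) stay in the primary TTP analysis. In section 3, state that they are not replaced.
3. Keep the analysis restricted to patients who complete treatment as exploratory.

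The separate low-cell-dose exclusion in 8.1.2 is not touched.

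The cost is a few sentences in an amendment, with no new visits, data or sample-size change. Section 5.9 already provides the follow-up: "Patients will be followed specifically for evidence of progression/recurrence based on imaging and survival". The downside is slight dilution of the TTP estimate by patients who received less than the full regimen.

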6.3 Gastrointestinal Toxicity

Nausea and/or vomiting should be controlled with adequate anti-emetic therapy. Prophylactic anti-emetic therapy can be used at the discretion of the treating physician. Patients are encouraged to take plenty of oral fluids. If symptoms persist despite maximal anti-emetic therapy, protocol drugs should be withheld until recovery to \leq grade 1.

Diarrhea should be managed with appropriate anti-diarrheal therapy. Patients should be encouraged to take plenty of oral fluids. If symptoms do not decrease to grade 1 or less with adequate anti-diarrheal therapy, all protocol drugs should be held until resolved to \leq grade 1.

6.4 Hypersensitivity Reactions

Caution: patients who had a mild to moderate hypersensitivity reaction have been successfully re-challenged, but careful attention to prophylaxis and bedside monitoring of vital signs is recommended.

Hypersensitivity reactions to IFN α and/or TLR3 ligand will be managed as follows:

Mild symptoms (e.g., mild flushing, rash, pruritus) - complete infusion, supervise at bedside, no treatment required.

Moderate symptoms (e.g., moderate rash, flushing, mild dyspnea, chest discomfort) - stop infusion, give intravenous diphenhydramine 25 mg and intravenous dexamethasone 10 mg, resume the infusion at a low rate after recovery of symptoms, then, if no further symptoms, at full dose rate until infusion is complete. If symptoms recur, stop the infusion and the patient should receive no additional INF α or TLR3 ligand for that cycle, but may be retreated after discussion with the Investigator. Keep a record of the toxicity.

Severe life threatening symptoms (e.g., hypotension requiring pressor therapy, angioedema, respiratory distress requiring bronchodilation therapy, generalized urticaria) - stop infusion, give intravenous diphenhydramine and dexamethasone as above, add epinephrine or bronchodilators if indicated. If wheezing is present, that is not responsive to bronchodilators, epinephrine is recommended. Patient should be removed from further protocol therapy. Report it as an adverse event.

7. ADVERSE EVENTS: LIST AND REPORTING REQUIREMENTS

Adverse event (AE) monitoring and reporting is a routine part of every clinical trial. The following list of AEs (Section 7.1) and the characteristics of an observed AE (Section 7.2) will determine whether the event requires expedited reporting **in addition** to routine reporting.

Note that Phase 2 of this study will include two periods of immunotherapy, administered before and after adjuvant chemotherapy (minimum 5 day wash-out periods), in order to separate potential toxicities of the chemokine modulatory regimen (all three factors are short-acting), from the anticipated toxicities of adjuvant chemotherapy. For this reason, we will only collect the toxicity data from the periods of immunotherapy. All toxicities related to the vaccine or CKM must be followed until resolution to grade 1 or baseline.

7.1 Adverse Events and Risks List(s)

7.1.1 DC Vaccine

Dendritic cell vaccines have been investigated extensively in a number of centers and to date, have not been reported to be associated with limiting toxicities or adverse side effects. DC vaccines carry a potential risk of development of autoimmune disease (such as lupus, or vitiligo). Whereas development of vitiligo has been reported with similar vaccines administered to melanoma patients (and correlated with positive response to vaccination), other side effects have not been reported. Although, based on previous trials with DC-based vaccines, the possibility of developing an allergic reaction to DC-based vaccines is rare there is a chance that patients could have an allergic reaction to the vaccine.

While other classes of immunotherapeutic drugs, particularly the currently approved immune checkpoint blocker, Yervoy [Ipilimumab] can produce significant toxicity, such as enterocolitis, hepatitis, dermatitis (including toxic epidermal necrolysis), neuropathy, and endocrinopathy, due to its ability to promote polyclonal T-cell activation and proliferation, such effects have not been described following application of DC cancer vaccines, including previously-administered alpha-DC1-based vaccines, their combinations with a long acting TLR3 ligand poly-ICLC (Okada,

Kalinski, Bartlett, J. Clin. Onc. 29 (3):330-336, 2011) or their combinations with the proposed CKM regimen in our patients treated on compassionate-use protocols.

